8.2.1. Pre-intervention administration procedures

8.2.1.1. Collection of demographic data

Demographic data such as date of birth (year only), age, sex, race, and ethnicity will be collected from each participant and recorded.

8.2.1.2. Medical/Vaccination history

Obtain the participant's medical/vaccination history by interviewing the participant and/or review of the participant's medical records. Record any pre-existing conditions, signs and/or symptoms present prior to the first dose of study intervention in the eCRF.

Medical history should be collected, recorded, and verified that all inclusion and none of the exclusion criteria related to medical and vaccination history (Section [5.2](#)) are met.

Both axillae will be examined for lymph nodes (swelling/tenderness) and unless exclusionary, if present, will be documented as medical history. Skin overlying both deltoid muscles for evidence of any findings that may confound local solicited AE assessments (e.g., rashes or tattoos) will be assessed, and if present, the participant will be excluded.

8.2.1.3. History-directed physical examination

History-directed physical examination will be performed. If the investigator determines that the participant's health on the day of the study intervention administration temporarily precludes dosing, the visit will be rescheduled (see Section 5.5).

8.2.1.4. Pregnancy test

Female participants of childbearing potential must perform a urine pregnancy test on the day of and before the administration of any dose of study intervention. Pregnancy testing must be done even if the participant is menstruating at the time of the study visit. The study intervention may only be administered if the pregnancy test is negative. If a prior serum test result is necessary as per IRB requirement, unless the sample is obtained on the day of study intervention, then a urine test must also be performed on the day of and prior to study intervention administration.

The urine pregnancy test kits (human chorionic gonadotropin [hCG] hormone test strip) provided to the study sites are approved by the FDA. Serum pregnancy testing, if required, will be performed as per standard of care.

Refer to Section 10.3.3.1 for the information on study continuation for participants who become pregnant during the study.

8.2.1.5. Warnings and precautions to administration of study intervention

Warnings and precautions to administration of study intervention must be checked at each visit with planned administration of study intervention. Refer to the approved product label/package insert for *Shingrix* and *Fluarix Quadrivalent*.

8.2.2. Study holding rules and safety monitoring

8.2.2.1. Safety review team oversight and staggered randomization

An internal GSK safety review team (SRT) which may also include staff from Moderna, will oversee the safety of this study. Randomization will be temporarily paused after 10% and 5% of participants in the HZ/su and mRNA booster cohort and Flu D-QIV and mRNA booster cohort, respectively, have received the study vaccinations at Visit 1 and been followed up for 7-days post-vaccination. Safety data for 7 days post-dosing will be reviewed for the HZ/suCoAd and FluD-QIVCoAd groups by the SRT at this pre-specified scheduled review. Randomization shall also be temporarily put on hold and an *ad hoc* SRT review will be performed if any of the holding rule criteria are met at any time during the study. Randomization can only be resumed following SRT approval to do so in the pre-specified scheduled or *ad hoc* SRT review.

The SRT will also perform safety reviews after all participants in the HZ/su and mRNA-1273 booster cohort sequential group have completed 14 days of follow-up after their HZ/su dose 1, and when all participants in the Flu D-QIV and mRNA-1273 cohort sequential group have completed 14 days of follow-up after their Flu D-QIV dose.

The SRT will also review all the safety data including solicited AEs, unsolicited AEs, SAEs, AESIs, IMCs, pIMDs, COVID-19 cases, pregnancies and suspected HZ cases at regular intervals during the conduct of the study while monitoring the safety holding rules (Section 8.2.2).

Any potential safety concern related to conduct of the study will be managed as per internal GSK process.

8.2.2.2. Study holding rules

Study holding rules are defined in **Table 13**. These holding rules are applicable only for the co-administration groups (HZ/suCoAd and FluD-QIVCoAd). If any study team member from a site, PPD, or GSK identifies that a holding rule criterion may have been met, they must inform the PPD MM immediately (by calling the 24 hours safety hotline number; see section 8.3.3.1), who will notify the SRT, and if confirmed, PPD will place study randomization on hold until the SRT has been able to review all applicable safety data and provided a decision on whether to continue with randomizations and the study as planned or otherwise. Moreover, if the investigator becomes aware of a holding rule (*e.g.*, 1a or 1d) being met, he/she must suspend administration of the study intervention and inform the PPD MM immediately. Further details of SRT processes are provided in the SRT Charter.

Table 13 Study holding rules

Holding Rule	Event	Number or Percentage of Participants	
		For HZ/suCoAd group	For FluD-QIVCoAd group
1a	Death or any life-threatening SAE that can be reasonably attributed to the vaccination	1 participant	1 participant
1b	Any non-life-threatening SAE that can be reasonably attributed to the vaccination	3/28 participants (for initial SRT review); For the rest of the study: 10%	3/25 participants (for initial SRT review); For the rest of the study: 10%
1c	Any withdrawal from the study (by investigator or participant request) following a Grade 3 AE that can be reasonably attributed to the vaccination	3/28 participants (for initial SRT review); For the rest of the study: 10%	3/25 participants (for initial SRT review); For the rest of the study: 10%
1d	Fever >40°C (104°F), OR Any solicited local event or solicited systemic AE leading to hospitalization, each within the 7-day (Days 1-7) post-vaccination period	2 participants	2 participants
2a	Any Grade 3 solicited systemic AE (lasting 48h or more) within the 7-day (Day 1-7) post-vaccination period	6/28 participants (for initial SRT review); For the rest of the study: 20%	5/25 participants (for initial SRT review); For the rest of the study: 20%
2b	Any Grade 3 unsolicited AE, that can be reasonably attributed to the vaccination, within the 7-day (Day 1-7) post-vaccination period	3/28 participants (for initial SRT review); For the rest of the study: 10%	3/25 participants (for initial SRT review); For the rest of the study: 10%

Risk assessment for study holding rules

Figure 2 illustrates that, with 28 participants per study group in the HZ/su and mRNA-1273 booster vaccine cohort at the pre-specified scheduled SRT review:

- Each holding rule 1a and 1d has more than 75% chance of not being met for vaccination with a true incidence rate of 1% and has more than 95% chance of being met for vaccination with a true incidence rate above 10%.
- Each holding rule 1b, 1c and 2b has more than 54% chance of not being met for vaccination with a true incidence rate below 10% and more than 81% chance of being met for vaccination with a true incidence rate above 15%.
- Each holding rule 2a has more than 76% chance of not being met for vaccination with a true incidence rate below 15% and more than 50% chance of being met for vaccination with a true incidence rate above 20%.

Figure 2 Evaluations based on 28 participants in the co-administration group in HZ/su and mRNA-1273 booster cohort risk assessment curve based on the proposed safety holding rules

[figure not shown]
[figure not shown]

Figure 3 illustrates that, with 25 participants per study group in the Flu D-QIV and mRNA-1273 booster vaccine cohort at the pre-specified scheduled SRT review:

- Each holding rule 1a and 1d has more than 78% chance of not being met for vaccination with a true incidence rate of 1% and has more than 73% chance of being met for vaccination with a true incidence rate above 10%.
- Each holding rule 1b, 1c and 2b has 54% chance of not being met for vaccination with a true incidence rate below 10% and has 75% chance of being met for vaccination with a true incidence rate above 15%.

- Each holding rule 2a has more than 68% chance of not being met for vaccination with a true incidence rate below 15% and more than 58% chance of being met for vaccination with a true incidence rate above 20%.

Figure 3 Evaluations based on 25 participants in the co-administration group in Flu D-QIV and mRNA-1273 booster cohort risk assessment curve based on the proposed safety holding rules

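### Two stated HZ/su holding-rule probabilities do not follow from Table 13: at n = 28 and a true 10% rate, rule 1d is met 78.5% of the time (not above 95%) and rules 1b, 1c and 2b are not met 45.9% of the time (not above 54%)

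*Protocol*

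**What the plan says.** Table 13 in Protocol section 8.2.2.2 sets the triggers for the HZ/suCoAd group. Rule 1a is met by "1 participant" and rule 1d by two. At the initial safety review team (SRT) review, rules 1b, 1c and 2b are met by 3 of 28, and rule 2a by 6 of 28.

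The risk assessment below the table describes how these rules behave "with 28 participants per study group in the HZ/su and mRNA-1273 booster vaccine cohort at the pre-specified scheduled SRT review". Two of its statements matter here:

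- Rules 1a and 1d are taken together, and each "has more than 95% chance of being met for vaccination with a true incidence rate above 10" percent.
- "Each holding rule 1b, 1c and 2b has more than 54% chance of not being met" when the true rate is below 10%.

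The parallel text for the Flu D-QIV cohort, at 25 participants, says of the same pair 1a and 1d that each "has more than 73% chance of being met for vaccination with a true incidence rate above 10" percent.

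**The concern.** The printed figures cannot all come from the same thresholds.

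- **Rule 1d.** Its trigger is two participants in both cohorts. The text has its chance of being met at a 10% rate rise from above 73% with 25 participants to above 95% with 28. Three more participants cannot do that.
- **Rules 1b, 1c and 2b.** Their trigger is three participants in both cohorts. The text gives the same 54% chance of not being met at 25 and at 28, although that probability must fall as the number observed rises.

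The section tells investigators, IRBs and the SRT how sensitive the first look is. Rule 1d covers fever above 40°C and solicited events leading to hospitalization. A reader would conclude that a 10% rate of such events fails to trigger rule 1d less than once in twenty first looks. The second figure has the opposite effect: it makes rules 1b, 1c and 2b look slower to trigger than they are.

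**Working it through.** **Inputs.** All come from Protocol section 8.2.2.2: n = 28 for HZ/suCoAd and n = 25 for FluD-QIVCoAd; triggers r = 1 (rule 1a), 2 (1d), 3 (1b, 1c, 2b), and 6 of 28 or 5 of 25 (2a). The true rates 1%, 10%, 15% and 20% are those the text uses.

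**Formula.** With X ~ Binomial(n, p), a rule is met with probability P(X ≥ r) and not met with probability P(X ≤ r − 1). The first rises with p and the second falls. A lower bound claimed for all rates above (or below) 10% is therefore governed by the value at 10%.

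**The protocol's own figures.** Where two rules share a figure, the lower bound is set by the weaker one.

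| Cohort, rule, event | Stated | Exact binomial |
|---|---|---|
| HZ/su 1a/1d, not met at 1% | >75% | 75.5% (1a), 96.8% (1d) |
| HZ/su 1a/1d, met at 10% | >95% | 94.8% (1a), **78.5% (1d)** |
| HZ/su 1b/1c/2b, not met at 10% | >54% | **45.9%** |
| HZ/su 1b/1c/2b, met at 15% | >81% | 81.3% |
| HZ/su 2a, not met at 15% | >76% | 76.5% |
| HZ/su 2a, met at 20% | >50% | 49.95% |
| Flu 1a/1d, not met at 1% | >78% | 77.8% (1a) |
| Flu 1a/1d, met at 10% | >73% | 92.8% (1a), 72.9% (1d) |
| Flu 1b/1c/2b, not met at 10% | 54% | 53.7% |
| Flu 1b/1c/2b, met at 15% | 75% | 74.6% |
| Flu 2a, not met at 15% | >68% | 68.2% |
| Flu 2a, met at 20% | >58% | 57.9% |

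All but the two bold values agree with the text to rounding. The method is therefore the protocol's own.

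**The two exceptions, n = 28 and p = 0.10.**

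- P(X = 0) = 0.9^28 = 0.0523
- P(X = 1) = 28 × 0.1 × 0.9^27 = 0.1628
- P(X = 2) = 378 × 0.1² × 0.9^26 = 0.2442

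Rule 1a is met with probability 1 − 0.0523 = 0.9477.

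Rule 1d is not met with probability P(X ≤ 1) = 0.2152, so it is met with probability 0.7848. P(X ≥ 2) reaches 0.95 only at a true rate of about 15.9%.

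Rules 1b, 1c and 2b are not met with probability P(X ≤ 2) = 0.4594, so they are met with probability 0.5406. The chance of not being met exceeds 54% only below a true rate of about 8.9%, so the claim fails from there up to 10%, inside the range it covers.

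**Variants.** With n = 27, 29 or 30, rule 1d is met 76.7%, 80.1% or 81.6% of the time, and rules 1b/1c/2b are not met 48.5%, 43.5% or 41.1% of the time. A Poisson approximation gives 76.9% and 47.0%. Raising each trigger by one does not help: rule 1d would then be met 54.1% of the time at 10%, and rules 1b/1c/2b only 62.3% at 15%, against the stated 81%.

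**The case against.** The case for leaving the text alone is that it is descriptive and little follows from it.

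- No Table 13 threshold depends on these figures.
- Under section 8.2.2.1, randomization pauses at the scheduled review whether or not a rule is met, and resumes only with SRT approval. A missed rule 1d trigger at that look does not let randomization continue unreviewed.
- Rule 1d is a plain count, and randomization is also put on hold "if any of the holding rule criteria are met at any time during the study". Its sensitivity therefore grows with accrual: at a 10% rate P(X ≥ 2) first reaches 95% at 46 co-administered participants (95.2%).
- The error for rules 1b, 1c and 2b is in the cautious direction.
- The SAP amendment (section 11) describes the safety interim analysis in the past tense, so a correction now mainly sets the record straight.

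These points are sound, and they limit the consequence. They do not make the two statements right. The participants beyond 28 are randomized only after the scheduled review, so later accrual cannot support a claim about that review.

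Figure 2 is not available in the text reviewed. Its curves may be correct; the error is shown for the prose only.

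**Conclusion.** Both statements are wrong as written for the review with 28 participants. At a true rate of 10%, rule 1d is met 78.5% of the time instead of more than 95%, a miss rate of 21.5% where the text implies under 5%. Rules 1b, 1c and 2b are not met 45.9% of the time instead of more than 54%; they are met 54.1% of the time where the text implies under 46%.

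The result rests on the Table 13 triggers and on independent participants with a common event rate, which is the model that reproduces the rest of the section. The 95% matches rule 1a alone. The 54% coincides both with the probability of being met at n = 28 and with the Flu D-QIV not-met figure at n = 25; which of these it came from cannot be established.

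The correction should be made because this text describes how the safety rules perform. It affects no rule, sample size or analysis.

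**What to change.** In the HZ/su part of the risk assessment in Protocol section 8.2.2.2:

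- **Rules 1a and 1d at a 10% rate.** Give about 95% met for rule 1a and 78.5% for rule 1d. Alternatively, state one shared lower bound of 78%, as the Flu D-QIV text does with 73%.
- **Rules 1b, 1c and 2b at a 10% rate.** Replace the 54% with 45.9% not met.

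Keep the lead-in that ties the figures to the scheduled review of 28 participants, so that they are read as first-look properties only. Check the Figure 2 curves against the same values. The other HZ/su figures and all the Flu D-QIV figures stand, and Table 13 is unchanged. The cost is two numbers in explanatory text.

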8.3. Adverse events (AEs), serious adverse events (SAEs) and other safety reporting

8.3.1. Time period and frequency for collecting AE, SAE and other safety information

The timeframes for collecting and reporting the safety information are provided in [Table 14](#).

Table 14 Timeframes for collecting and reporting of safety information

EVENT	TIMING OF REPORTING
Local and systemic solicited events	Day 1 through Day 7 following each study intervention administration (see Figure 1)
Unsolicited AEs	Day 1 through Day 30 following each study intervention administration (see Figure 1)
AEs/SAEs leading to withdrawal from the study	Day 1 following study intervention administration through Phone Contact 2 study conclusion
All SAEs including SAEs related to the study intervention	Day 1 following study intervention administration through Phone Contact 2 study conclusion
AEs/SAEs related to study participation or SAEs related to concurrent GlaxoSmithKline medication/vaccine	Enrollment (i.e., signing ICF) through Phone Contact 2 study conclusion
IMCs, AESIs, COVID-19 cases, and in HZ/su and mRNA-1273 booster cohort only, also pIMDs and suspected HZ episodes	Day 1 following study intervention administration through Phone Contact 2 study conclusion
Pregnancy	Day 1 through Phone Contact 2 study conclusion

The investigator or designee will record and immediately report all SAEs/AESIs/pIMDs/pregnancies in study participants to PPD via the Expedited AE Reporting Form or pregnancy form (as applicable). Reporting should, under no circumstances, occur later than 24 hours after the investigator becomes aware of an SAE/AESI/pIMD/pregnancy, as indicated in Section [10.2.12](#). The investigator will submit any updated SAE/AESI/pIMD/pregnancy data to PPD within 24 hours of it being available.

A post-study AE/SAE is defined as any event that occurs outside of the AE/SAE reporting periods defined in [Table 14](#). Investigators are not obligated to actively seek AEs or SAEs from former study participants. However, if the investigator learns of any SAE, including a death, at any time after a participant has been discharged from the study, and he/she considers the event to be reasonably related to a study intervention, the investigator will promptly notify the study contact for reporting SAEs mentioned in [Table 16](#).

8.3.2. Method of detecting AEs and SAEs, pregnancies and other events

Detection and recording of AEs/SAEs/AESIs/pIMDs/pregnancies are detailed in Section [10.2.10](#).

Assessment of AE/SAE/AESI/pIMD intensity, causality and outcome are described in Section [10.2.11](#).

Open-ended and non-leading verbal questioning of participants is the preferred method of acquiring information related to an AE/SAE/AESI/pIMD/pregnancy.

8.3.3. Regulatory reporting requirements for SAEs, pregnancies and other events

Once an investigator (or designee) becomes aware that a study participant has experienced an SAE/AESI/pIMD/pregnancy, it must be reported to PPD using the required documentation and within the timeframes mentioned in [Table 15](#). This is essential for meeting GSK and Moderna legal obligations and ethical responsibilities for participant safety and the safety of a study intervention under clinical investigation.

For SAEs/AESIs/pIMDs, the investigator must always provide an assessment of causality at the time of the initial report, as defined in the Section [10.2.11.2](#).

Local regulatory requirements, GSK and Moderna policy for preparation of an investigator safety report of Suspected Unexpected Serious Adverse Reactions (SUSAR) must be followed. These reports will be forwarded to investigators as necessary.

GSK and Moderna have the legal responsibility to notify both local and other applicable authorities/regulatory agencies about the safety of an investigational study intervention under their IND. GSK and Moderna will comply with country-specific regulatory requirements related to safety reporting to the regulatory authority, IRB and investigators.

An investigator who receives an investigator safety report describing an SAE or other specific safety information (e.g., summary or listing of SAEs) from PPD will review and then file it along with the IB and will notify the IRBs, if appropriate according to local requirements.

Please refer to Section 10.2.12 for further details regarding the reporting of SAEs/AESIs/pIMDs/pregnancies.

Table 15 Timeframes for submitting SAE, AESI, pIMD, and pregnancy reports to PPD

Type of event	Initial reports		Follow-up of relevant information on a previous report	
	Timeframe	Documents	Timeframe	Documents
SAEs	24 hours*	electronic Expedited Adverse Events Report	24 hours*	electronic Expedited Adverse Events Report
Pregnancies	24 hours*	electronic pregnancy report	24 hours*	electronic pregnancy report
AESIs	24 hours**	electronic Expedited Adverse Events Report	24 hours*	electronic Expedited Adverse Events Report
pIMDs	24 hours**	electronic Expedited Adverse Events Report	24 hours*	electronic Expedited Adverse Events Report

*Timeframe allowed after receipt or awareness of the information by the investigator/site staff.

**Timeframe allowed once the investigator determines that the event meets the protocol definition of an AESI or pIMD.

8.3.4. Treatment of AEs

Any medication administered for the treatment of an SAE/AESI/pIMD should be recorded in the Expedited Adverse Event Report of the participant's eCRF screen (refer to Section 10.2.12.1).

8.3.5. Participant card

The investigator (or designee) must provide the participant with a “participant card” containing information about the clinical study. The participant must be instructed to always keep the participant card in their possession for the duration of the study. In an emergency, this card serves to inform the responsible attending physician/caregiver/family member that the participant is in a clinical study and that relevant information may be obtained by contacting the investigator or his/her back-up.

8.3.6. Medical device deficiencies

One of the study interventions, the seasonal influenza vaccine, Flu D-QIV, is presented as a pre-filled syringe and according to the FDA regulations [FDA, 2018] is within scope of device reporting in clinical trials as a combination product constituted of a device and biologic product (e.g., pre-filled syringes). Refer to the [Glossary of terms](#) for the definition of the combination product and medical device deficiencies. Device-related incidents fulfilling the definition of an AE/SAE will also follow the processes outlined in Section [10.4](#).

8.3.6.1. Detection, follow-up, and prompt reporting of medical device deficiency

The investigator is responsible for the detection, documentation and prompt reporting of any medical device deficiency occurring during the study to PPD. This applies to any medical device provided for the conduct of the study.

Device deficiencies will be reported to PPD within 24 hours after the investigator determines that the event meets the protocol definition of a device deficiency.

The investigator will ensure that follow-up includes any additional investigations to elucidate the nature and/or relatedness of the device deficiency to the incident. Follow-up applies to all participants, including those who discontinue study intervention or the study.

New or updated information will be recorded on the originally completed form with all changes signed and dated by the investigator and also reported to PPD.

Refer to Section [10.4](#) for definitions and details on recording and reporting of these events.

8.3.6.2. Regulatory reporting of medical device deficiency when used as combination product

The investigator will promptly report all device deficiencies occurring with any medical device provided for use in the study to PPD. GSK has a legal responsibility to notify appropriate regulatory authorities and other entities about safety information linked to medical devices being used in clinical studies. Refer to Section [10.4.3](#) for details of reporting.

The investigator, or responsible person according to local requirements (e.g., the head of the medical institution), will comply with the applicable local regulatory requirements relating to the reporting of device deficiencies to the IRB.

